3.A. Neuropsychological Educational Approach to Cognitive Remediation (NEAR, termed CR+Bridging). This study proposes to use the Neuropsychological Educational Approach to Cognitive Remediation (NEAR¹⁰ as an adjunct to usual treatment) developed by [name] (Consultant on this SPIRE application; see letter of support) to target the cognitive control and decision-making/problem-solving deficits associated with suicidal behavior in MDD. CR+Bridging is a manualized treatment program (group format) based on empirically-supported principles of learning and motivation. It is a recovery-oriented rehabilitation approach that provides a focus on cognitive skills but does so by taking into account the social-emotional variables which impact and interact with "thinking" throughout the day. The sessions consist of computerized executive functioning (EF) exercises, followed immediately by a Bridging group to discuss effective strategies for transferring the EF skills exercised to real-life situations. NEAR has been shown to be effective in other psychiatric populations, including schizophrenia and bipolar disorder.³⁸ It results in significant improvement in attention/executive functioning skills, including problem-solving^{36, 39} and cognitive control.⁴⁰ These remediation effects have been shown to persist for at least four months post intervention and translate to improvements in symptoms, real-world problem solving, social functioning, and occupational functioning.³⁸

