Iowa Gambling Task¹¹⁻¹² (with alternate decks)	Problem-solving	X	X	X
Tower of Hanoi ⁵⁰ (with parallel versions)	Problem-solving	X	X	X
Stroop Test ⁵¹ (with parallel versions)	Cognitive inhibition	X	X	X
Go/No-Go ⁵² (with parallel versions)	Motor inhibition	X	X	X
Naming Test/Neuropsychological Assessment Battery, ¹⁴ Form 1 & 2 (Control test; not expected to change with intervention)	Naming/Control test	X	X	X
Montgomery-Ashberg Depression Rating Scale¹³	Depression	X	X	X
The Personal & Social Performance Scale ²	Social	X	X	X
The Work & Social Adjustment Scale ³	Social, Occupational	X	X	X
Questionnaire for assessing the impact of the COVID-19 pandemic and accompanying mitigation efforts on older adults ¹⁵	Impact of COVID-19	X	X	X
Longitudinal Interval Follow-up Evaluation Range of Impaired Functioning Tool, LIFE-RIFT ¹⁶	Functional impairment	X	X	X

3.E. CR+Bridging Training, Fidelity, Acceptability, and Feasibility. Members of our research team (Drs. [name] and [name]) have extensive experience developing psychosocial interventions in civilian and Veteran samples and establishing their fidelity. CR+Bridging training will include weekly supervision of [name] with [name] or [name] and a modified version of the Cognitive Remediation Fidelity Scale¹⁰ (see **Appendix 6**) will be employed to assess fidelity to the manual. [name] will also oversee implementation of supplementary measures of potential moderators of the intervention (e.g., motivation for treatment and baseline sets of work habits,⁴⁸ quality of therapeutic relationships⁴⁹).

Acceptability will be examined via survey responses (see **Appendix 5**) completed by the patients and therapist at the completion of the intervention and follow-up (Weeks 10 and 20). Feasibility will be measured in

several ways. This includes: (1) ease of implementation—operationalized as less than 60 hours per cycle from start/preparation through intervention delivery until conclusion of follow-up assessment; (2) recruitment, attendance, and retention (operationalized as >75% successful recruitment and 75% attend >15 sessions); and (3) training and fidelity of therapist to CR+Bridging will be conducted at Week 10 (see **Appendix 6**).

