Aim 1: Sample size: Definitive conclusions about the efficacy of the CR+Bridging intervention cannot be made based on this pilot study's findings. We plan to use the data collected to: (1) calculate power for a larger confirmatory study and (2) examine acceptability and feasibility data. We plan to submit a VA Merit application that will involve a rigorous RCT to determine efficacy of this novel intervention.

Analysis: We will calculate descriptive statistics, e.g., means, standard deviations, minimum, maximum for continuous measures (e.g., CR+Bridging treatment fidelity ratings, retention), as well as count and frequencies for categorical measures (e.g., attendance). We will be able to compare these descriptive statistics to published rates of recruitment, engagement, and attendance of similar type interventions.

Aim 2: Sample Size: Using a two-sided paired t-test to compare MADRS¹³ before and after for each subject, for 90% power at a 5% level of significance and assuming a decrease in MADRS with a range of standard deviations from 1 to 10, we can detect a mean paired difference of -0.7 to -6.5 for 22 Veterans.

Analysis: MADRS¹³ and Iowa Gambling Task (IGT^{11, 12}) scores are the primary outcome variables here. For all of the study completers, each outcome measure will be compared initially between Baseline and Week 10 (pre- vs. post-intervention) by paired t-test. As a secondary analysis, all outcome measures in Table 3.D will be compared this way as well. Correction for multiple comparisons will be performed using a Holm's correction.

For exploratory analyses, outcome variables that reach significance for Pre-tx/Baseline vs. Post-tx/Week 10 comparisons will also be analyzed across all three time points (Baseline, Week 10, Week 20/Follow-up) using a linear mixed-effects model with unstructured correlation between time points.

Missing data will be assumed to be missing at random and handled accordingly by multiple imputation. All statistical tests will be 2-tailed with alpha=0.05.

Aim 3: Sample Size: This aim is exploratory. We will utilize the same sample size as shown in the sample size section and acknowledge that we may be underpowered for these analyses.

Analysis: Each outcome measure (e.g., QACPOA¹⁵, LIFE-RIFT¹⁶) will be compared initially between Baseline and Week 10 by a paired t-test and if either show significance, then they will be compared across all three time points using the same mixed-effects model analysis as described in Aim 2.

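### The only Week 20 outcome analysis is restricted to outcomes already significant at Week 10, so other outcomes (including, by design, the naming control test) have no Week 20 comparison and those that pass are overestimated

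*Combined protocol and SAP*

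**What the plan says.** Section 3.G, Aim 2, runs the Week 10 comparison without any condition: "each outcome measure will be compared initially between Baseline and Week 10 (pre- vs. post-intervention) by paired t-test", and as a secondary analysis "all outcome measures in Table 3.D will be compared this way as well". The Week 20 analysis is conditional. It is labelled exploratory, and "outcome variables that reach significance for Pre-tx/Baseline vs. Post-tx/Week 10 comparisons will also be analyzed across all three time points", "using a linear mixed-effects model with unstructured correlation between time points". Aim 3 sets a similar condition for measures such as the COVID-19 questionnaire and LIFE-RIFT: "if either show significance, then they will be compared across all three time points using the same mixed-effects model analysis". A Holm correction is planned, but the text gives neither the family of tests nor whether the gate uses raw or Holm-adjusted p-values.

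Table 3.D schedules 13 outcome measures at Baseline and Week 10. Twelve of them are also measured at Week 20; the Intrinsic Motivation Inventory is not. The naming test is one of the twelve and is annotated "Control test; not expected to change with intervention". The examples given for Aim 1's descriptive statistics are fidelity, retention and attendance, not outcome scores at Week 20.

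**The concern.** Week 20 is the study's only look at whether gains last, and the visit is in person for every participant. Section 3.A rests part of the rationale on durability: "These remediation effects have been shown to persist for at least four months post intervention". The gate has three consequences.

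1. An outcome that misses at Week 10 has no specified Week 20 comparison. That could be the Iowa Gambling Task, one of the two primary outcomes, or any outcome whose gain develops after treatment ends.
2. The naming test is the only designated control measure in a single-arm study. If it behaves as intended it fails the gate, so a maintained gain elsewhere has no Week 20 control result to set beside it.
3. An outcome that passes does so partly because its Week 10 change came out high by chance. The Week 20 change shares the same baseline, so it is also inflated, but less. A truly stable effect then looks large and fading.

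The Week 10 results are not affected, so the Week 10 inputs for planning the later RCT are safe.

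**Working it through.** **Inputs from the documents (Section 3.G).** Mean paired difference 3.2; SD of differences 4.35; two-sided alpha 0.05; 22 completers from 36 enrolled with up to 40% attrition (36 × 0.6 = 21.6).

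**Assumptions.** The correlation ρ between the Week 10 and Week 20 change scores is not given. I take 0.5, with a range of 0.3 to 0.7. The value 0.5 follows if the three visits have equal variances and equal correlations. The true change is the same at both later visits unless stated. Data are complete, in which case the unstructured model's Week 20 contrast equals the mean paired change.

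**The plan's own figure.** Noncentrality = √22 × 3.2/4.35 = 4.690 × 0.7356 = 3.45. Against the critical t of 2.08 on 21 df, power is 90.8%. The stated 22 for 90% power reproduces. This power is also the chance that an outcome with the planned effect passes an unadjusted gate.

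**Bias among outcomes that pass.** With equal SDs for the two changes,

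- Week 20 excess ≈ ρ × (mean Week 10 change given passing − true change)
- apparent loss from Week 10 to Week 20 ≈ (1 − ρ) × the same bracket

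For a true change of 1.6, the simulated Week 10 mean given passing is 2.49, so the bracket is 0.89. With ρ = 0.5 the formula gives an excess of 0.5 × 0.89 = 0.45; direct simulation gives 0.44.

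Simulation with 200,000 trials per row, n = 22, SD 4.35, ρ = 0.5 (excess for ρ = 0.3 to 0.7 in brackets):

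| Gate | True change | Pass | Week 10 mean if passing | Week 20 mean if passing | Week 20 excess |
|---|---|---|---|---|---|
| 0.05 | 3.2 | 91% | 3.35 | 3.28 | 0.08 (0.05 to 0.11) |
| 0.05 | 2.4 | 69% | 2.85 | 2.62 | 0.22 (0.14 to 0.31) |
| 0.05 | 1.6 | 38% | 2.49 | 2.04 | 0.44 (0.26 to 0.63) |
| 0.025 | 3.2 | 84% | 3.45 | 3.32 | 0.12 (0.08 to 0.17) |
| 0.025 | 1.6 | 27% | 2.67 | 2.14 | 0.54 (0.32 to 0.75) |
| 0.05/13 | 3.2 | 59% | 3.76 | 3.48 | 0.28 (0.17 to 0.39) |
| 0.05/13 | 1.6 | 9% | 3.09 | 2.35 | 0.75 (0.46 to 1.05) |

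The 0.025 gate is the first Holm step for two primary outcomes. The 0.05/13 = 0.0038 gate is the first step if all 13 repeated outcomes form one family. Both families are assumptions. Without a gate, the Week 20 mean equals the true value in every scenario (1.60 for 1.6 and 3.20 for 3.2, for example). If all 36 complete, the pass rates at the planned effect are 99%, 98% and 90% for the three gates.

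**Outcomes left without a Week 20 analysis** (n = 22, unadjusted gate):

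- Naming test with no true change: modelled in 5% of trials, so omitted in 95%. At 0.05/13 it is modelled in 0.4%.
- Effect of 3.2 present only at Week 20: also modelled in 5%.
- Effect of 3.2 at Week 20, half-developed (1.6) at Week 10: modelled in 38%.
- An ungated Week 20 paired comparison has 91% power in the last two cases, by the same calculation as the plan's own figure.

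**The case against.** The best defence is that the model asks a follow-on question, whether a gain already detected is maintained, and that gating such a question is a common choice. The analysis is labelled exploratory, the pilot makes no claim to settle efficacy, and at the only effect size in the documents the bias under a raw gate is 0.08 of 3.2 points. That last point stands: for MADRS at its planned effect, bias is no reason to change the plan unless the gate is Holm-adjusted over a large family. The 0.05/13 row is the strictest case; the two-primary family is much milder.

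Other points also have some force. No passage predicts an effect that first appears at Week 20. The plan does not state a Week 20 role for the naming test, and its Week 10 comparison is intact. Week 20 is ten weeks after treatment, so it could not confirm four-month persistence with or without the gate. Aim 3's wording could send both measures forward when one passes. Aim 1's descriptive list is only by way of example, so it does not rule out Week 20 summaries, though it does not promise any.

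None of this supplies a Week 20 comparison for an outcome that misses. The exploratory label weakens the case for a gate, because there is no confirmatory claim to protect.

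**Conclusion.** The concern holds, as a minor point. The omission follows directly from the text and needs no assumption about correlation: outcomes that miss at Week 10 have no specified Week 20 comparison, and the control test is expected to be among them (95% of the time at an unadjusted 0.05 if it truly does not change). Aim 3's ambiguous wording is the one partial exception.

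The bias is secondary and applies only to outcomes that pass. It is about 2% of the true change at the planned MADRS effect with an unadjusted gate, and more than a quarter (0.44 of 1.6) at half that effect. It grows as the gate becomes stricter. Its size depends on the assumed change-score correlation, complete data and, for the Holm rows, the assumed family; its direction is the same across the range examined.

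**What to change.** Remove the condition on Week 10 significance from the exploratory paragraph of Aim 2 and from the Aim 3 analysis. Fit the three-time-point model already specified to all 12 outcomes measured at Baseline, Week 10 and Week 20, whatever their Week 10 p-values: C-SSRS, Ruminative Response Scale, Iowa Gambling Task, Tower of Hanoi, Stroop, Go/No-Go, naming test, MADRS, Personal and Social Performance, Work and Social Adjustment, the COVID-19 impact questionnaire and LIFE-RIFT. Report Week 20 versus Baseline and Week 20 versus Week 10 for each, with 95% confidence intervals, labelled exploratory. The question of raw or adjusted p-values at the gate then disappears, as does the ambiguity in Aim 3. Name the C-SSRS score to be modelled; the planned Week 10 t-test needs that in any case.

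The cost is two short edits and a few more fits of an existing model. No new data, visits or participants are needed. The downside is a longer exploratory table (12 × 2 = 24 contrasts), with no added confirmatory claim.
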